3.3 Inclusion and Exclusion Criteria

The target population of the parent study is sedentary older adults, with minor depressive symptoms. Individuals expressing an interest in participating after recruitment out-reach will be screened in-person (e.g., at HRC or at participant's home). As a part of the parent study, participants will complete several assessments to confirm that they meet the following inclusion criteria.

Inclusion Criteria

- Men and women aged ≥ 65 years
- Self-reporting ≥ 8 hours of sitting per/day (e.g., sedentary behavior)
- Depressive symptoms (defined as ≥ 4 and < 16 points on the center for epidemiological studies depression-scale)

Exclusion criteria have been selected to ensure safety and optimize compliance, while minimizing confounds due to overt disease or conditions that may significantly influence study outcomes. Exclusions may be during the in-person screening as described below:

Exclusion Criteria

- Unwilling to follow the study protocol
- A median daily step count $> 7,500$ steps per day (as measured by the ActiGraph), or per discretion of the PI
- Cognitive impairment (defined as Montreal Cognitive Assessment,³⁷ MoCA < 22 points)
- Self-reporting a history of inflammatory bowel disease/syndrome, major depression, bipolar, schizophrenia, or other psychotic or neurological disorders (e.g., Parkinson's disease), or per discretion of the PI
- Self-reporting type one or type two diabetes
- Allergic to intervention or control products
- Recent use (within the last 3 months) of antibiotics, or per discretion of the PI
- Recent use (within the last 3 months) of probiotics, or per discretion of the PI
- Current substance use disorder (Drug Abuse Screening Test,^{40,41} DAST-10 > 2 points)
- Current alcohol use disorder (Alcohol Use Disorders Identification Test,^{42,43} AUDIT-C ≥ 4 points)
- Unstable anti-depressant use (e.g., change in medication within last 3-6 months), or per discretion of the PI
- Current homicidal or suicidal ideation (assessed via the P4 Suicidality Screener⁴⁴)
- Current psychosis (via the Psychosis and Hallucinations Questionnaire,⁴⁵ PsychHQ > 12 points)
- Manic symptoms (assessed by the Mood Disorder Questionnaire,⁴⁶ MDQ > 5 points)

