5.1 Participant Visit Schedule

All study visits will take place at the Clinical Research Laboratory at HRC, Roslindale, MA, an HRC-affiliated housing site, or at the participants home (if possible).

Participant eligibility will be determined during an in-person screening that is a part of the parent study. If eligible and interested, the participant will be asked to continue with 5 additional visits. The assessments/activities for the study visits pertaining to this specific ancillary study are outlined below. Some measures (e.g., safety measures) will overlap with the parent study and are indicated with a *.

The majority of subjects that will enroll in this ancillary study will undergo screening as a part of the parent study as outlined in **IRB Pro00064749**. However, if a participant wants to enroll only in this ancillary study, the participant will need to undergo the telephone screening and in-person screening visits as outlined in the parent study (**IRB Pro00064749**).

Visits

Assessments and Medication Administration at Each Visit

Baseline Visit, Week 0:	Assessments/Activities: 1. Turn in Diet Records* 2. Provide Fecal Sample 3. Depressive Symptoms 4. Positive/Negative Affect 5. Suicidal Ideation* 6. Symptoms*
Week 4 Visit:	Assessments/Activities 1. Turn in Diet Records* 2. Depressive Symptoms 3. Positive/Negative Affect 4. Suicidal Ideation* 5. Symptoms* 6. Compliance*
Week 8 Visit:	Assessments/Activities 1. Turn in Diet Records* 2. Depressive Symptoms 3. Positive/Negative Affect 4. Suicidal Ideation* 5. Symptoms* 6. Compliance*
Week 12 Visit:	Assessments/Activities: 1. Turn in Diet Records* 2. Provide Fecal Sample 3. Depressive Symptoms 4. Positive/Negative Affect 5. Suicidal Ideation* 6. Symptoms* 7. Compliance*

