5.2 Study Visits and Assessments

A summary of this ancillary study's assessments is provided in the table below. Given that this is a pilot study, we will allow for flexibility for the administration of some assessments at visits, as long as these changes do not impede the scientific interpretation.

Assessment	Baseline	4 Weeks	8 Weeks	12 Weeks
Fecal Sample	X			X
Suicidal Ideation (via P4SS)*	X	X	X	X
Depression Severity (via CES-D)	X	X	X	X
3-Day Diet Record*	X	X	X	X
Relevant Symptoms*	X	X	X	X
Positive and Negative Affect	X	X	X	X
Compliance*		X	X	X

* Reflects that this measure is also a part of the parent study

The parent study consists of up to 6 study visits: a screening visit, a baseline visit, 3 mid-point visits, and a final follow-up visit. The ancillary study adds additional assessments to the baseline visit, 2 of the 3 mid-point visits, and the follow-up visit in week 12. Information on the study procedures at the study visits related to the ancillary study is outlined below.

Informed Consent: In order to participate in this study, all interested and eligible participants will be required to provide informed consent. They will be given ample time to ask any questions about the study. A trained research staff will answer any questions and if the individual is interested in participating in the study, they will be offered to sign the informed consent form. When the staff is confident that the participant is completely

familiar with the document and understands all the aspects of the informed consent form, it should be signed by the participant in the presence of the staff member, and should then be signed by the staff member. All consent forms will be double checked to make sure they are properly signed and dated. Copies of completed consent forms will be given to the participant and the original signed document will be kept on file at the Hinda and Arthur Marcus Institute for Aging Research. As a part of the informed consent process, potential participants will be clearly informed that this intervention is not a treatment option for depressive symptoms or depression, but rather studying feasibility of a dietary strategy for health. If seeking a treatment, they will be directed to their primary care.

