6.1 Statistical Analysis

All analyses will be performed by intent to treat, and further evaluated per protocol. As a first step, we will assess distribution characteristics of the primary and secondary outcomes. Where appropriate, transformation of variables to combat skew or other irregularities will be employed. Participant characteristics will be summarized using means, medians, standard deviations, interquartile regions and ranges for continuous variables and sample counts and proportions generated for discrete characteristics. Comparability of treatment arms will be assessed on potentially confounding characteristics using tabular and graphical methods.

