6.2 Aim Statistical Methods and Power

Aim 1 Hypothesis: The abundance of microbes that produce SCFA increase after 12 weeks of dietary fiber and anthocyanin supplementation compared to placebo. **Aim 1 Analysis:** To determine taxa and pathways that differ significantly by treatment (blueberry vs. placebo powder), multivariate analyses that accounts for covariates will be carried out using MaAsLin2⁶³ (Multivariate Analysis by Linear Models). MaAsLin2 performs a mixed-effects linear regression of individual log-transformed microbial features (response) on categorical or continuous factors (explanatory variables). A random effects model will be used for repeated measures (i.e., longitudinal data). Linear models will be constructed to assess each feature independently, and adjusted for false discovery using Benjamini-Hochberg FDR. The output of MaAsLin will reveal whether cohort participants with different dietary exposures also differ in relative abundance of a particular bacterial species or pathway in the gut. **Aim 1 Expected Results/Power:** With our proposed sample size of 20/group, we anticipate power 0.95 to detect a 0.314-unit difference in common taxa (~14310 sequences and 0.0954 relative abundance at 5% read usage rate), and a 0.122-unit difference in rare taxa (~2222 sequences and 0.0148 relative abundance at 5% read usage rate) collected at the 2 time points. Approximating as above, the corresponding detection limit for 250 pathways is power 0.95 for a 0.0013-unit difference (1282 sequences at a 33% read usage rate). We assumed we will observe 250 pathways.

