Aim 2 Hypothesis: The fecal SCFA's increase after 12 weeks of dietary fiber and anthocyanin supplementation compared to placebo. **Aim 2 Analysis:** Since butyrate is implicated as the gut-derived metabolite important for depression,³⁰ we will focus on the change in fecal butyrate, but others SCFA and combinations will be explored. Change in fecal butyrate will be calculated between baseline and the final 12 week follow-up. Distribution of change will be summarized using sample quantities and kernel density estimates. We will develop 80% confidence interval estimates of inter- and intra- individual variation (i.e., standard deviation) of change in fecal butyrate, the upper limit will be used to estimate sample size calculations for a subsequent clinical trial. Formal inference and estimation of treatment effects will use a Student's t-test to compare mean change in fecal butyrate in the intervention group compared to placebo. **Aim 2 Expected Results/Power:** A 12 week intervention in non-depressed older adults supplementing usual diet with prebiotic fiber, report mean percent of fecal butyrate concentration increased by 0.4%.⁶⁴ Assuming standard deviation of mean percent change of fecal butyrate = 0.32% and an alpha=0.05, a sample size of 20/group is required to detect a 0.3% change in fecal butyrate.

Aim 3 Hypothesis: Depressive symptom severity (evaluated by CES-D) declines after 12 weeks of dietary fiber and anthocyanin supplementation compared to placebo. **Aim 3 Analysis:** Change in depressive symptom severity (CES-D) will be calculated between baseline and the final 12 week follow-up (we will consider change between baseline and visits at week 4 and 8). The same analyses described for Aim 2, will be implemented for Aim 3. **Aim 3 Expected Results/Power:** Other lifestyle interventions, including dietary strategies, that were designed to reduce depressive symptoms report between a 2-4 point reduction in CES-D scores.⁶⁵⁻⁶⁷ Assuming standard deviation of change of depressive symptoms = 3.5 estimated from other lifestyle interventions and an alpha=0.05, a sample size of 20/group is needed to detect a 2 point reduction in CES-D scores.

CHAPTER 7 DATA MANAGEMENT AND QUALITY

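### Aims 2 and 3 compare unadjusted change from baseline; adjusting week 12 for its own baseline costs little and is more precise if the baseline slope is clearly below 1

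*Combined protocol and SAP*

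**What the plan says.** Section 6.2 (Aim 2) defines the outcome as the change in fecal butyrate from baseline to week 12. Formal inference is a "t-test to compare mean change in fecal butyrate in the intervention group compared to placebo". For CES-D, section 6.2 says: "The same analyses described for Aim 2, will be implemented for Aim 3". Section 5.4 names depressive symptom severity as the primary endpoint, so this rule also governs the main comparison.

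No covariate is named for Aim 2 or Aim 3. For Aim 1, by contrast, "multivariate analyses that accounts for covariates will be carried out". Section 6.1 states: "Comparability of treatment arms will be assessed on potentially confounding characteristics using tabular and graphical methods". It attaches no analytic consequence to what those tables and graphs show.

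Both baseline values are already scheduled. The week-0 visit in section 5.1 includes "Provide Fecal Sample", and the assessment table in section 5.2 has CES-D at baseline and weeks 4, 8 and 12.

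**The concern.** A comparison of mean change is a comparison of week-12 means with the whole baseline difference subtracted, that is, with a baseline coefficient of exactly 1. Nothing in the document suggests that this coefficient is near the best one for either outcome. If the true slope of week 12 on baseline is below 1, each unit of chance imbalance between arms in the outcome's own baseline passes into the estimate at (1 − slope) and adds to its variance. Better precision and protection against chance imbalance are therefore the same benefit and should not be counted twice.

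What is at stake is the width of the intervals in a trial of 40 people. There is also a question of pre-specification: if section 6.1's tables show a baseline difference, an adjusted model added afterwards would look data-driven.

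**Working it through.** **Inputs from the document.** 20 per group; alpha 0.05 (sidedness not stated, two-sided used). Aim 2: SD of change 0.32, difference 0.3. Aim 3: "Assuming standard deviation of change of depressive symptoms = 3.5 estimated from other lifestyle interventions", difference 2 points. CES-D at entry is "defined as ≥ 4 and < 16 points on the center for epidemiological studies depression-scale".

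**Inputs assumed.** The document gives no baseline SD and no baseline-to-week-12 slope or correlation. For CES-D I take a baseline SD s0 of 2.5 to 3.45. The upper value is the SD of an even spread over the integers 4 to 15, √((12² − 1)/12) = 3.45. The eligibility score is taken at screening, so the week-0 SD may differ. Slopes b run from 0.51 to 1. The value 0.51 is only an illustrative low value: section 5.2 gives it as a test-retest reliability of the CESD-R, but the source cited is dated 1983 and the CESD-R reference 2004, so it is not evidence for this trial's slope.

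**The plan's own figures first (t-test on change, 38 df, 80% power assumed because none is stated).**
- Aim 2: 19 per group are needed, and power at 20 per group is 0.824. The stated 20 per group reproduces.
- Aim 3: SE = 3.5 × √(2/20) = 1.107; 95% half-width = 2.024 × 1.107 = 2.24 points; power for 2 points = 0.421. About 50 per group are needed for 80%. The stated 20 per group does not reproduce. That is a separate issue.

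**Formulas for the adjusted model (37 df).**
- Imbalance share of the change-score variance = (1 − b)² s0² / 3.5²
- Variance ratio, adjusted to change = (1 − share) × 37/36. The factor 37/36 = 1.028 is the average cost of estimating the slope.
- Power from the noncentral t with 37 df.

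Example, b = 0.51, s0 = 3.45: share = 0.49² × 3.45² / 12.25 = 0.233; ratio = 0.767 × 1.028 = 0.788; SE = 1.107 × √0.788 = 0.983; half-width = 2.026 × 0.983 = 1.99.

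**CES-D results (s0 = 2.5 to s0 = 3.45; t-test power 0.421, half-width 2.24).**

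| Slope | Imbalance share | Variance ratio | Power for 2 points | Half-width |
|---|---|---|---|---|
| 0.51 | 12%–23% | 0.902–0.788 | 0.458–0.509 | 2.13–1.99 |
| 0.7 | 5%–9% | 0.981–0.938 | 0.428–0.443 | 2.22–2.17 |
| 0.8 | 2%–4% | 1.007–0.988 | 0.419–0.425 | 2.25–2.23 |
| 0.9 | at most 1% | 1.023–1.018 | 0.413–0.415 | 2.27–2.26 |
| 1 (worst case) | 0 | 1.028 | 0.412 | 2.27 |

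**Break-even slope in variance.** Setting the ratio to 1 gives b = 1 − (3.5/s0) × √(1/37), which is 0.770 at s0 = 2.5 and 0.833 at s0 = 3.45. Adjustment gains below that slope.

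**Checks.** The cells imply a week-12 SD of 3.5 to 4.9 and a correlation of 0.36 to 0.70, which is feasible because eligibility limits screening scores, not week-12 scores. Simulation at slopes 0.51, 0.7, 0.9 and 1 (40,000 trials per cell) agreed within 0.005 for power and 0.006 for the ratios. Type I error was 0.048–0.051 for both methods.

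**Butyrate.** Only the worst case can be bounded from the document: with b = 1, power for 0.3 falls from 0.824 to 0.813.

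**The case against.** The strongest reply is that nothing here is an error. The t-test on change is unbiased and keeps its alpha under randomisation, and section 6.2 is consistent in defining, describing, testing and sizing on the same change score. A difference in mean changes does not assert that the slope is 1; it is only possibly less precise. That is correct, and it limits the point to efficiency.

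The benefit also cannot be established from the document. In the table it is small except at the lowest slope, and it depends on the assumed baseline SD. With s0 = 2.0, a slope of 0.51 gives power of only 0.440, a slope of 0.7 gives 0.422 (no real gain), and break-even drops to 0.71. With s0 = 1.5, even a slope of 0.51 gives just 0.427. Assuming equal baseline and week-12 variances instead moves break-even up to 0.94–0.95, but at a slope of 0.9 that needs a baseline SD of 3.5/√0.2 = 7.8, which is hard to square with screening scores of 4 to 15. So the break-even range is an assumption, not a property of this trial. This objection stands as to size.

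Three further points stand. No gain is shown for butyrate, whose analysis scale is left open by the transformation clause in section 6.1. The cost grows with dropout: at 16 per group the factor is 1 + 1/28, or 3.6%. And the pilot's stated planning output is the variation in change (sections 6.2 and 8.6), which must not be lost. None of these removes the asymmetry for CES-D: a loss of about 0.01 in power at worst, against a possible gain of up to about 0.09 in the cases shown.

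**Conclusion.** The concern holds as a point of efficiency, not validity. Aims 2 and 3 use unadjusted change with no covariate, although both baselines are collected. For CES-D at 20 per group, adjustment changes power for 2 points by between −0.009 (slope 1) and +0.088 (slope 0.51, baseline SD 3.45). At a slope of 0.7 the gain is 0.007 to 0.022. These figures rest on the document's SD of change of 3.5, an assumed baseline SD of 2.5 to 3.45, a linear slope common to both arms, two-sided alpha of 0.05 and no dropout. The actual gain is unknown for both outcomes. Power for 2 points stays between 0.41 and 0.51 in every case tabulated, so adjustment is no answer to the Aim 3 sample-size shortfall. The change is worth making because its cost is small and bounded; the trial is not invalid without it.

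**What to change.** In section 6.2, for Aims 2 and 3, make the primary inference a linear model of the week-12 value, on its chosen scale, with arm and the outcome's own baseline value as terms. Fix this before unblinding and report the adjusted arm difference with its confidence interval. Keep the SD of change and its 80% interval as the planning output. Also report the residual SD and the baseline-to-week-12 correlation, which the next trial would need to size a baseline-adjusted analysis.

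The cost is one sentence of analysis text, one model term and one degree of freedom (38 to 37). If the true slope is 1, variance rises by 2.8%, CES-D power for 2 points goes from 0.421 to 0.412, and butyrate power for 0.3 from 0.824 to 0.813. No new data, visits or participants are needed.

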7.1 Data Management Plan

All data collected for analysis will be de-identified and assigned a unique study number. Any data collected on paper forms will be kept in a locked file cabinet at HRC. Data collected on paper forms will be entered and stored on a password-protected secure server at HRC. When possible, data will be collected directly via our electronic data capture system (e.g, REDCap).

Expected data type: this project includes both digital and non-digital data. Non-digital data may include hand-written questionnaires and dietary records that will be collected on/by each participant, as well as intervention compliance (via physical return of used/un-used packets). All non-digital data, will be documented and transferred to a digital database (e.g., REDCap) that is used for secure data acquisition and storage. Digital

data will include the genomic sequences of the gut microbiota acquired from the fecal and powder samples, as well as quantification of fecal short chain fatty acids. All data from this study will be primary data.

Data format: Non-digital data acquired from this study will be kept as paper forms, but also will be transferred to our data capture/storage software, REDCap. The Marcus Institute for Aging Research (Marcus Institute) primarily employs the REDCap system to facilitate digital data management operations. REDCap is a full-featured clinical trials data management system (DMS) accessible to data entry and data analysis workstations using secure Web technologies. The REDCap product is developed and maintained by Vanderbilt University in cooperation with REDCap Consortium members, including our institute. Hebrew SeniorLife hosts and maintains a dedicated instance of REDCap for use across our research enterprise. REDCap has the added benefit of offering data exportation of the datasets into several various spreadsheet-type formats (e.g., .csv, .xml, .r, .pdf, .sps, etc.). To transpose non-digital data to digital formats, questionnaires will be transferred to our study-specific, secure REDCap database. Some questionnaires may be captured digitally in real-time, via direct data capture with an iPad that uploads the data to our secure REDCap database. For the data that is not directly captured or entered into REDCap, the data will have to be merged into a master data file. Dietary records will first be entered into dietary analytic software (Nutrition Data System for Research, NDSR), utilizing required formats. Once all data is entered into NDSR, it will be exported into an spreadsheet-type format, (e.g., excel to produce a .csv file) to facilitate data merging and long-term storage in the REDCap database. The other digital data gathered from fecal samples (e.g., quantification of short chain fatty acid and abundances of specific microbes) will be stored in a spreadsheet-like format (e.g., .csv) to facilitate data merging with the data stored on REDCap. All data related to this project will be merged into a final master dataset that will be used for analyses and will contain enough information to allow independent use of the data. The various types of formats provided by REDCap (e.g., .csv, .xml, .r, .pdf, .sps, etc.) will help ensure that the data will be readily accessible and usable datasets in community-recognized standard and machine-readable formats.

Data storage and preservation: During the intervention, any data collected on paper forms will be transposed to the digital data capture software (e.g., REDCap) as soon as possible. The de-identified, non-digital data (e.g., paper forms) collected as a result of this study will be stored in a locked cabinet at the Marcus Institute, and the PI will be responsible for the key to the cabinet. Only approved individuals (e.g., study staff) will be able to access the paper forms in the locked cabinet. For long-term preservation, digital data will be stored indefinitely on the secure server employed by the Marcus Institute, that will be accessible by qualified individuals (e.g., study staff and monitors of the USDA). Paper forms will be stored for at least 5 years following the completion of this study. The final digital dataset will be uploaded to a secure, password-protected digital cloud (e.g., ShareFile) to avoid loss of data.

Data sharing, protection, and public access: Data resulting from this study will be shared upon request. Individuals that would like to use de-identified data may do so providing the appropriate approvals are acquired (e.g., IRB). To protect the confidentiality of the participants of this study, we will make the identifiable data and associated documentation available to users under a data-sharing agreement that provides for: 1) a commitment to using data only for research purposes and not to identify any particular participant; 2) a commitment to securing the data using appropriate computer technology; and 3) a commitment to destroying or returning the data after analyses are completed. The availability of data will be advertised over the Internet through websites maintained by Hebrew SeniorLife and Harvard Medical School. All investigators wishing to access the data will submit a brief proposal to [name] describing their research project, data needs, regulatory approvals (e.g., IRB and USDA approval), and mechanisms to assure patient confidentiality. Upon affirmative review by the PI and co-investigators of this study, a data-sharing agreement will be signed and the requesting investigators will be given a working electronic data file and appropriate documentation. Although identifiable information will be collected, the master data file will be de-identified to avoid breach of confidentiality. All recruited individuals will be given a unique study ID number that will be used in place of identifiable information when possible. To minimize the risk of breach in confidentiality, all computer datasets that contain personal identifiers (e.g., name, address, and phone numbers) will be stored in a separate encrypted dataset. The pass phrase to gain access to the encrypted files will be known only to qualified individuals (e.g., the PI, data analyst, and research staff). Any form or printout that contains personal identifiers will be stored under lock and key. All digital data will be entered and stored on a password-protected secure

server at Marcus Institute. Each research study is provided separate project workspace on REDCap, in which all of the study data are stored in a MySQL relational database on the private corporate network behind several firewalls and located physically within the Hebrew SeniorLife data center.

